4.1 Study/project specific decisions

For each study (or project) various issues need to be addressed and specified in the protocol or RAP documentation. Any deviations from protocol must be discussed and defined at the latest in the RAP documentation.

The proposed primary analysis and potential sensitivity analyses should be discussed and agreed with the health authorities and documented in the protocol (or at the latest in the RAP documentation before database lock).

4.2 End of treatment phase completion

Patients **may** voluntarily withdraw from the study treatment or may be taken off the study treatment at the discretion of the investigator at any time. For patients who are lost to follow-up, the investigator or designee should show "due diligence" by documenting in the source documents steps taken to contact the patient, e.g., dates of telephone calls, registered letters, etc.

The end of treatment visit and its associated assessments should occur within 7 days of the last study treatment.

Patients may discontinue study treatment for any of the following reasons:

- Adverse event(s)
- Lost to follow-up
- Physician decision
- Pregnancy
- Protocol deviation
- Technical problems
- Subject/guardian decision
- Death
- Progressive disease
- Study terminated by the sponsor
- Non-compliant with study treatment

Page 193

- No longer requires treatment
- Treatment duration completed as per protocol (optional, to be used if only a fixed number of cycles is given)

Death is a reason which "must" lead to discontinuation of the patient from the trial.

4.3 End of post-treatment follow-up (study phase completion)

End of post-treatment follow-up visit will be completed after discontinuation of study treatment and post-treatment evaluations but prior to collecting survival follow-up.

Patients may provide study phase completion information for one of the following reasons:

- Adverse event
- Lost to follow-up
- Physician decision
- Pregnancy
- Protocol deviation
- Technical problems
- Subject/guardian decision
- Death
- Progressive disease
- Study terminated by the sponsor

4.4 Medical validation of programmed overall lesion response

In order to be as objective as possible, the RECIST programmed calculated response assessment is very strict regarding measurement methods (i.e. any assessment with more or less sensitive method than the one used to assess the lesion at baseline is considered UNK) and not available evaluations (i.e. if any target or non-target lesion was not evaluated the whole overall lesion response is UNK unless remaining lesions qualified for PD). This contrasts with the slightly more flexible guidance given to local investigators (and to the central reviewers) to use expert judgement in determining response in these types of situations, and therefore as a consequence, discrepancies between the different sources of response assessment often arise. To ensure the quality of response assessments from the local site and/or the central reviewer, the responses may be re-evaluated by clinicians (based on local investigator data recorded in the eCRF or based on central reviewer data entered in the database) at Novartis or external experts. In addition, data review reports will be available to identify assessments for which the investigators' or central reader's opinion does not match the programmed calculated response based on RECIST criteria. This may be queried for clarification. However, the investigator or central reader's response assessment will never be overruled.

If Novartis elect to invalidate an overall lesion response as evaluated by the investigator or central reader upon internal or external review of the data, the calculated overall lesion response at that specific assessment is to be kept in a dataset. This must be clearly documented in the RAP documentation and agreed before database lock. This dataset should be created and stored as part of the 'raw' data.

Any discontinuation due to 'Disease progression' without documentation of progression by RECIST criteria should be carefully reviewed. Only patients with documented deterioration of symptoms indicative of progression of disease should have this reason for discontinuation of treatment or study evaluation.

4.5 Programming rules

The following should be used for programming of efficacy results:

4.5.1 Calculation of 'time to event' variables

Time to event = end date - start date + 1 (in days)

When no post-baseline tumor assessments are available, the date of randomization/start of treatment will be used as end date (duration = 1 day) when time is to be censored at last tumor assessment, i.e. time to event variables can never be negative.

4.5.2 Incomplete assessment dates

All investigation dates (e.g. X-ray, CT scan) must be completed with day, month and year.

If one or more investigation dates are incomplete but other investigation dates are available, this/these incomplete date(s) are not considered for calculation of the assessment date (and assessment date is calculated as outlined in Section 3.2.8). If all measurement dates have no day recorded, the 1st of the month is used.

If the month is not completed, for any of the investigations, the respective assessment will be considered to be at the date which is exactly between previous and following assessment. If a previous and following assessment is not available, this assessment will not be used for any calculation.

4.5.3 Incomplete dates for last known date patient alive or death

All dates must be completed with day, month and year. If the day is missing, the 15th of the month will be used for incomplete death dates or dates of last contact.

4.5.4 Non-target lesion response

If no non-target lesions are identified at baseline (and therefore not followed throughout the study), the non-target lesion response at each assessment will be considered 'not applicable (NA)'.

4.5.5 Study/project specific programming

The standard analysis programs need to be adapted for each study/project.

4.5.6 Censoring reason

In order to summarize the various reasons for censoring, the following categories will be calculated for each time to event variable based on the treatment completion page, the study evaluation completion page and the survival page.

For survival the following censoring reasons are possible:

- Alive
- Lost to follow-up

For PFS and TTP (and therefore duration of responses) the following censoring reasons are possible:

- Ongoing without event
- Lost to follow-up
- Withdrew consent
- Adequate assessment no longer available*
- Event documented after two or more missing tumor assessments (optional, see Table 3-2)
- Death due to reason other than underlying cancer (only used for TTP and duration of response)
- Initiation of new anti-cancer therapy
- *Adequate assessment is defined in Section 3.2.8. This reason is applicable when adequate evaluations are missing for a specified period prior to data cut-off (or prior to any other censoring reason) corresponding to the unavailability of two or more planned tumor assessments prior to the cut-off date. The following clarifications concerning this reason should also be noted:
- This may be when there has been a definite decision to stop evaluation (e.g. reason="Sponsor decision" on study evaluation completion page), when patients are not followed for progression after treatment completion or when only UNK assessments are available just prior to data cut-off).
- The reason "Adequate assessment no longer available" also prevails in situations when another censoring reason (e.g. withdrawal of consent, loss to follow-up or alternative anticancer therapy) has occurred more than the specified period following the last adequate assessment.
- This reason will also be used to censor in case of no baseline assessment.

5 References (available upon request)

Dent S, Zee (2001) application of a new multinomial phase II stopping rule using response and early progression, J Clin Oncol; 19: 785-791.

Eisenhauer E, et al (2009) New response evaluation criteria in solid tumors: revised RECIST guideline (version 1.1). European Journal of Cancer, Vol.45: 228-47.

Ellis S, et al (2008) Analysis of duration of response in oncology trials. Contemp Clin Trials 2008; 29: 456-465.

EMA Guidance: 2012 Guideline on the evaluation of anticancer medicinal products in man

FDA Guidelines: 2005 Clinical Trial Endpoints for the Approval of Cancer Drugs and Biologics, April 2005.

This statistical analysis plan (SAP) describes all planned analyses for the Clinical Study Report (CSR) of extension phase of study CBYL719X2402, a phase II, multicenter, open-label, three-cohort, non-comparative study to assess the efficacy and safety of alpelisib plus fulvestrant or letrozole in patients with PIK3CA mutant, hormone receptor (HR) positive, HER2- negative advanced breast cancer (aBC), who have progressed on or after prior treatments.

The content of this SAP is based on protocol CBYL719X2402 V06. All decisions regarding final analysis, as defined in the SAP document, have been made prior to database lock.

1.1 Study design

This is a phase II, multicenter, open-label, three-cohort, non-comparative study of alpelisib plus endocrine therapy (either fulvestrant or letrozole) in patients with HR+, HER2-negative aBC harboring PIK3CA mutation(s) in the tumor whose disease has progressed on or after prior treatments. Gonadal suppression must be achieved with either goserelin or leuprolide in men (cohort B) and premenopausal women patients.

Patients must have the PIK3CA mutation to be eligible for the trial. Patients will be required to sign a molecular pre-screening consent to have their mutational status either analyzed by providing adequate tumor tissue or if PIK3CA status is known, providing tumor tissue to confirm PIK3CA mutational status using a Novartis designated central laboratory. This will be conducted during a pre-screening phase prior to enrolling into the trial by Day -21. Approximately 1300 patients are expected to be pre-screened to identify PIK3CA mutational status. Those patients that harbor the PIK3CA mutation are eligible for the study and will then have the opportunity to sign the main ICF to begin screening procedures to determine eligibility. Overall approximately 340 patients (112 in each cohort), with HR+, HER2-negative aBC harboring a PIK3CA mutation in tumor tissue, that has progressed on or after prior treatments are expected to be enrolled.

The study will be composed of 2 phases:

Core Phase: includes treatment phase for all patients from First Patient First Treatment (FPFT) until 18 months post Last Patient First Treatment (LPFT) + 1 month Safety follow-up (total 19 months post LPFT)

Extension Phase: includes treatment phase starting at the end of the treatment Core Phase until Last Patient Last Visit (LPLV) (up to 36 months); The extension treatment phase is only for patients who are continuing to benefit from treatment at the end of the Core Phase who are not eligible for PSDS (Post-Study Drug Supply) in their country based on local regulations. Patients will continue on their existing treatment assigned in the Core Phase until discontinuation or Last Patient Last Treatment (LPLT) of the Extension Phase. Note: If PSDS becomes available for a patient, the patient should be discontinued from the study and access treatment via PSDS.

Patients who are benefiting from treatment and are eligible for PSDS will exit the trial at the end of the Core Phase. At the start of the Core Phase, patients will be assigned to a cohort based on previous therapy (AI or fulvestrant) as indicated below:

[figure not shown]
Cohort A: Patients who received any CDK 4/6 inhibitor plus any AI as immediate prior treatment will receive alpelisib + fulvestrant

Cohort B: Patients who received any CDK 4/6 inhibitor plus fulvestrant as immediate prior treatment will receive alpelisib + letrozole

Cohort C: Patients who received systemic chemotherapy or ET (as monotherapy or in combination with targeted treatment except CDK 4/6i + AI) as immediate prior treatment will receive alpelisib + fulvestrant

Note: In Cohort C, ET includes letrozole, fulvestrant and CDK4/6 inhibitor plus fulvestrant.

Figure 1-1 Study Design

Treatment crossover between cohorts will not be permitted in this study.

The primary objective of the study is to assess the proportion of patients who are alive without disease progression at 6 months based on local investigator assessment per RECIST v1.1 separately in Cohorts A and C (alpelisib in combination with fulvestrant) and Cohort B (alpelisib in combination with letrozole) among patients with HR+, HER2-negative aBC harboring a PIK3CA mutation who have progressed on or after prior treatments.

The primary analysis for each cohort will be performed 6 months after the last patient enrolled in that specific cohort has started treatment. The final analysis will be performed after LPLV of the study which include cumulative data (eg safety and clinical benefit) since the start of Core Phase for the patients who enter the Extension Phase.

2 Statistical methods

2.1 Data analysis general information

The final analysis will be performed by Novartis and/or a designated CRO. SAS version 9.4 or later software will be used to perform all data analyses and to generate tables, figures and listings.

Data included in the analysis

The analysis cut-off date for the first interim analysis of study data will be established after at least **CC1** patients receiving Alpelisib + Fulvestrant (cohort A) have at least 6 months of follow-up. The analysis cut-off date for the second interim analysis of study data will be established after at least **CC1** patients have been treated (regardless of cohort) and have at least 6 months of follow-up on study. The third IA will be performed after the Core Phase has ended.

The analysis cut-off date for the primary analysis of each cohort will be established 6 months after the last patient enrolled in that cohort has started treatment. The final analysis will be performed after LPLV of the study which include cumulative data (eg safety and clinical benefit) since the start of Core Phase for the patients who enter the Extension Phase.

All statistical analyses will be performed using all data collected in the database up to the data cutoff date. All data with an assessment date or event start date (e.g. vital sign assessment date or start date of an adverse event) prior to or on the cut-off date will be included in the analysis. Any data collected beyond the cut-off date will not be included in the analysis and will not be used for any derivations.

All events with start date before or on the cut-off date and end date after the cut-off date will be reported as 'ongoing'. The same rule will be applied to events starting before or on the cut-off date and not having documented end date. This approach applies, in particular, to adverse event and concomitant medication reports. For these events, the end date will not be imputed and therefore will not appear in the listings.

For the purpose of reporting in the extension phase, the subject data from Cohort A and Cohort C will be pooled together.

All analysis will be performed from the first dose of study treatment in Core phase until the end of Extension Phase.

For all main analysis, the CSR SAP, version CBYL719X2402_SAP_Amendment 4 needs to be referred to.

General analysis conventions

Pooling of centers: Unless specified otherwise, data from all study centers will be pooled for the analysis. Due to expected small number of patients enrolled at centers, no center effect will be assessed. Protocol deviations, number of patients in analysis populations and discontinuations from study treatment will be summarized by country.

Qualitative data (e.g., gender, race, etc.) will be summarized by means of contingency tables separately for each cohort a missing category will be included as applicable. Percentages will

be calculated using the number of patients in the relevant population or subgroup as the denominator.

Quantitative data (e.g., age, body weight, etc.) will be summarized by appropriate descriptive statistics (i.e. mean, standard deviation, Q1, median, Q3, minimum, and maximum) separately for each cohort.

Safety summaries (tables, figures) include only data from the on-treatment period with the exception of baseline data which will also be summarized where appropriate (e.g. change from baseline summaries). In addition, a separate summary for death including on treatment and post treatment deaths will be provided. In particular, summary tables for adverse events (AEs) will summarize only on-treatment events, with a start date during the on-treatment period (*treatment-emergent* AEs).

However, all safety data (including those from the post-treatment period) will be listed and those collected during the pre-treatment and post-treatment period will be flagged.

2.2 Analysis sets

Safety Set in Extension Phase

The **Safety set in Extension Phase** includes all patients who received at least one dose of any component of the study treatment in Extension Phase. Patients will be analyzed according to the study treatment actually received.

The actual treatment received corresponds to:

1. the assigned treatment if patients took at least one dose of that treatment.
2. the first treatment received if the assigned treatment was never received.

All analysis will be performed on safety set in extension phase.

2.3 Basic demographic and background data

All demographic and baseline disease characteristics data will be summarized and listed by cohort. Categorical data (e.g. gender, age groups: <65 and \geq 65 years, race, ethnicity, Child bearing status, ECOG performance status) will be summarized by frequency counts and percentages; the number and percentage of patients with missing data will be provided. Continuous data (e.g. age, weight, height, body mass index) will be summarized by descriptive statistics (N, mean, median, standard deviation, Q1, Q3, minimum and maximum). BMI (kg/m^2) will be calculated as $\text{weight}[\text{kg}] / (\text{height}[\text{m}]^2)$ using weight and height at Baseline.

2.4 Patient disposition in Extension Phase

Patient disposition in Extension Phase will be summarized using the Safety Set in Extension Phase. The following summaries will be provided:

- Number (%) of patients who are still on-treatment in Extension Phase (based on the 'End of Extension Treatment Phase' page not completed);
- Number (%) of patients who discontinued the Extension study treatment phase (based on the 'End of ExtensionTreatment Phase' page)

- Primary reason for Extension study treatment phase discontinuation (based on the 'End of Extension Treatment Phase' page)

2.5 Prior, concomitant and post therapies

Prior anti-cancer therapy

The number and percentage of patients who received any prior anti-neoplastic surgery will be summarized by system organ class and preferred term for all patients.

The safety set for extension phase will be used for all anti cancer therapy tables.

Concomitant medications

Concomitant therapy is defined as all interventions (therapeutic treatments and procedures) other than the study treatment administered to a patient coinciding with the study treatment period. Concomitant therapy include medications (other than study drugs) starting on or after the start date of study treatment or medications starting prior to the start date of study treatment and continuing after the start date of study treatment.

Concomitant medications will be coded using the World Health Organization (WHO) Drug Reference Listing (DRL) dictionary that employs the WHO Anatomical Therapeutic Chemical (ATC) classification system and summarized by lowest ATC class and preferred term using frequency counts and percentages. Surgical and medical procedures will be coded using MedDRA and summarized by SOC and preferred term. These summaries will include:

- Medications starting on or after the start of study treatment but no later than 30 days after start of last dose of study treatment and
- Medications starting prior to start of study treatment and continuing after the start of study treatment.

All concomitant therapies will be listed. Any concomitant therapies starting and ending prior to the start of study treatment or starting more than 30 days after the last date of study treatment will be flagged in the listing. The safety set for extension phase will be used for all concomitant medication tables and listings.

2.6 Extension Phase Clinical Benefit

The secondary objective related to the Extension Phase of the study is to evaluate clinical benefit as assessed by the Investigator. Proportion of patients with clinical benefit is defined by the number of patients with clinical benefit as assessed by investigator during Extension Phase (begins after the end of the Core Phase) divided by the number of patients in Extension Phase (Safety set in Extension Phase).

Proportion of patients with clinical benefit as assessed by the investigator will be summarized at scheduled visits. Clinical benefit will be summarized using the Safety Set in Extension Phase.

2.7 Safety data for Extension Phase

Safety analyses for the Extension Phase will be performed on the Safety Set in Extension Phase. The assessment of safety will be based mainly on the duration of exposure and dosage. The following summaries will be provided since the start of Core Phase:

- Duration of exposure to study treatment;
- Dose of study treatment received;
- Dose adjustments and discontinuation of study treatment.

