To evaluate the safety and tolerability of the combination for each cohort.	Type, frequency and severity of adverse events per CTCAE v4.03 Type, frequency and severity of laboratory toxicities per CTCAE v4.03	

Objective	Endpoint	Analysis
Evaluate clinical benefit as assessed by the Investigator during the Extension Phase	Proportion of patients with clinical benefit as assessed by the Investigator at scheduled visits	

Sign main ICF and

perform screening

procedures

(Day -21 to -1)

4 Study design

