7.2.2 Safety and tolerability assessments

Core Phase:

Safety will be monitored by assessing physical examination, vital signs, performance status evaluation, ECG, cardiac imaging, laboratory evaluations for hematology and biochemistry, including glucose monitoring as well as collecting of the adverse events at every visit. For details on AE collection and reporting, refer to Section 8.

If one of the study drugs is being held due to toxicity, scheduled visits and assessments should still be performed as described in Table 7-1.

Extension Phase:

Safety assessments in the Extension Phase will consist of monitoring and recording all AEs including SAEs, refer to Section 8.

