10.5.2 Safety objectives

10.5.2.1 Analysis set and grouping for the analyses

For all safety analyses, the safety set will be used. All listings and tables will be presented for each cohort.

The assessment of safety will be based mainly on the frequency of adverse events and on the number of laboratory values that fall outside of pre-determined ranges. Other safety data (e.g., ECG, vital signs) will be considered as appropriate. All safety data will be listed.

The overall observation period will be divided into three mutually exclusive segments:

- 1. pre-treatment period: from day of patient's informed consent to the day before first dose of study medication,
- 2. on-treatment period: from day of first dose of study medication to 30 days after last dose of study medication,
- 3. post-treatment period: starting at day 31 after last dose of study medication.

The safety summary tables will include only assessments collected no later than 30 days after study treatment discontinuation, with the exception of summary table for all deaths. Those collected later than 30 days after study treatment discontinuation will be flagged in listings.

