10.5.2.2 Adverse events (AEs)

Summary tables for adverse events (AEs) will include only AEs that started or worsened during the on-treatment period, the *treatment-emergent* AEs.

The incidence of treatment-emergent adverse events (new or worsening from baseline) will be summarized by system organ class and or preferred term, severity (based on CTCAE grades), type of adverse event, relation to study treatment. Deaths reportable as Serious Adverse Events and non-fatal serious adverse events will be listed by patient and tabulated by type of adverse event and cohort.

Serious adverse events, non-serious adverse events and adverse events of special interest (AESI) during the on-treatment period will be tabulated.

All deaths (on-treatment and post-treatment) will be summarized.

All AEs, deaths and serious adverse events (including those from the pre and post-treatment periods) will be listed and those collected during the pre-treatment and post-treatment period will be flagged.

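### The Extension SAP rests safety mainly on exposure and dose, names no SAE, AESI or treatment-related AE table, and pools Cohorts A and C, against the protocol's AE-based, per-cohort safety plan

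*SAP*

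**What the plan says.** The SAP document holds two plans: the Extension Phase SAP, written to protocol version 06, and the main CSR SAP, Amendment 4, written to version 05.

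**Basis of the safety assessment.** Extension SAP 2.7 says "The assessment of safety will be based mainly on the duration of exposure and dosage". It then lists three summaries: length of exposure, dose received, and dose adjustments with discontinuations. Protocol 10.5.2.1 says "The assessment of safety will be based mainly on the frequency of adverse events and on the number of laboratory values" outside set ranges. For the Extension in particular, protocol 7.2.2 says "Safety assessments in the Extension Phase will consist of monitoring and recording all AEs including SAEs".

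**Tables.** Protocol 10.5.2.2 says "Serious adverse events, non-serious adverse events and adverse events of special interest (AESI) during the on-treatment period will be tabulated". It also asks for incidence by relation to study treatment, and for SAEs to be tabulated by cohort. Extension SAP 2.8 plans treatment-emergent AEs by system organ class, preferred term and maximum CTCAE grade, and a listing that carries relationship and outcome. Section 2.1 adds a death summary, and section 2.4 tabulates the main reason for stopping Extension treatment.

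**Cohorts.** The safety objective in protocol Table 3-1 is "To evaluate the safety and tolerability of the combination for each cohort", and 10.5.2.1 requires all safety tables and listings cohort by cohort. Extension SAP 2.1 says that, for Extension reporting, "the subject data from Cohort A and Cohort C will be pooled together". The general conventions in the same section still call for summaries of each cohort on its own, and section 2.3 says "All demographic and baseline disease characteristics data will be summarized and listed by cohort".

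**The concern.** Time on drug, among patients selected because they are still benefiting, describes persistence more than harm. In the Extension the protocol drops scheduled central laboratory tests, ECGs and protocol imaging, so AE recording is the main safety information left. A plan that ranks exposure and dose above it reverses the protocol's order.

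Without a split by seriousness or by relationship, and without AESI groupings, a reader of the final report would have to rebuild those counts from listings for the longest-treated patients. The third interim analysis stops at the end of the Core Phase (protocol 10.7), so events that arise in the Extension are reported only in the final analysis that this SAP governs.

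Pooling A with C removes the unit in which the safety objective is stated, and the Extension SAP gives no reason for it.

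**Working it through.** No sample size, power or event count is involved, so the check is a comparison of text.

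| Item | Protocol | Extension SAP | Main SAP, Amendment 4 |
|---|---|---|---|
| Main basis of safety | AE frequency and laboratory values (10.5.2.1) | Exposure and dose (2.7) | AE frequency and laboratory values overall (2.8); exposure and dose for the Extension (2.8.5) |
| AEs by SOC, PT, grade | Required (10.5.2.2) | Planned (2.8) | Planned (2.8.1) |
| SAE table | Required (10.5.2.2) | Not named | Planned (2.8.1) |
| AESI table | Required (10.5.2.2) | Not named | Planned (2.8.1.1) |
| AEs by relationship | Required (10.5.2.2) | Listing only (2.8) | Planned (2.8.1) |
| AEs leading to discontinuation | No table named | Not named; main reason for stopping in 2.4 | Planned (2.8.1) |
| Deaths | Required (10.5.2.2) | Summary planned (2.1) | Planned (2.8.2) |
| Display | Each cohort (Table 3-1, 10.5.2.1) | A and C pooled (2.1); by cohort (2.1 conventions, 2.3) | Each cohort (2.8) |

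1. *Basis.* Extension SAP 2.7 and protocol 10.5.2.1 each say what safety rests on mainly, and they name different things. The SAP is also uneven within itself: 2.8 plans AE incidence tables that 2.7 does not treat as the main evidence.

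2. *Tables.* The AE text of Extension SAP 2.8 follows main SAP 2.8.1 closely but ends before the paragraph that lists summaries by relationship, seriousness, discontinuation and dose change. Nothing elsewhere in the Extension SAP names an SAE, AESI or treatment-related AE table.

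3. *Does the pointer supply them?* Extension SAP 2.1 sends the reader to Amendment 4 for the main analysis. Four things stop that from clearly importing the tables. The Extension SAP introduction claims to cover every analysis planned for the Extension report. Its section 2.2 runs every analysis on the Extension safety set, whereas main SAP 2.8 uses the overall Safety Set. The Extension section of Amendment 4 itself, 2.8.5, repeats the exposure-and-dose sentence with the same three summaries. And if the pointer imported all AE tables, Extension SAP 2.8 would have no purpose.

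4. *Cohorts.* Under the pooling rule the reporting groups are A+C and B. The protocol asks for A, B and C. The Extension SAP has no section on changes to protocol-specified analyses, and section 4 of the main SAP records only COVID-19 changes.

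**The case against.** The other side has real points.

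- *AE analysis is planned.* A reader might infer that the final report would leave serious or related events out of its tables altogether. It would not: every treatment-emergent AE enters the 2.8 tables, the listing carries relationship and outcome, deaths are summarised, and reasons for stopping are tabulated. What is missing is the breakdown by seriousness, relationship and AESI. Maximum grade does not replace seriousness; protocol 8.1.2.1, in its text on laboratory abnormalities, notes that a severe grade does not by itself make an event serious.
- *Dose data have a protocol role.* Protocol 10.5.2.6 studies tolerability through reductions and interruptions due to AEs. That supports keeping the 2.7 summaries, but not making them the main basis.
- *Pooling keeps the regimens apart.* A and C both receive alpelisib plus fulvestrant, and B is not pooled. A reader might infer that no result by cohort survives; the loss is confined to A and C separately. Nor are the cohort instructions unworkable, since the specific pooling rule can be read as overriding the general conventions. They need clarifying.
- *Discontinuation tables.* A reader might take their absence as a breach of the protocol. The protocol names no such table, so this is a departure from main SAP practice only.
- *The AE section is an addition.* The Extension part of Amendment 4 (2.8.5) has no AE tables of its own, so the Extension SAP improves on it. That is true, but it still falls short of protocol 10.5.2.2.
- *Small set.* With few patients, listings recover much of what extra tables would show. This limits the consequence without resolving the contradiction.

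**Conclusion.** The point stands. Three departures from the protocol are in the text: the stated main basis of safety, the unnamed SAE, AESI and treatment-related AE tables, and the unexplained pooling of A and C. The second depends on reading the pointer to Amendment 4 as not importing those tables. The text favours that reading but does not settle it.

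The effect is confined to the Extension Phase safety report. No hypothesis test and no primary result is touched, and Core Phase safety by cohort is covered by the main SAP. It is worth correcting before the final report, but it does not threaten the study's main conclusions.

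No percentage is claimed. A reader might be tempted to use the 21 and 9 patients that the protocol's Amendment 5 and Amendment 6 summaries report as still on treatment in January 2022. Those are not the Extension set. They count everyone on treatment, and only benefiting patients without access to post-study drug supply enter. They also appear to precede the end of Core treatment: enrollment was complete by 14-Dec-2020 and Core treatment runs 18 months past the last first treatment, which is about mid-2022 if that treatment fell close to the enrollment date. The size of the Extension set is not stated.

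**What to change.** 1. Reword Extension SAP 2.7 so that safety rests mainly on the frequency, severity and seriousness of AEs, with exposure and dose as supportive summaries.
2. Name SAE, AESI and treatment-related AE tables on the Safety Set in Extension Phase, reusing the shells behind main SAP 2.8.1 and 2.8.1.1. Tables of AEs leading to discontinuation or dose change may be added from the same shells; the protocol does not require them.
3. Show Cohorts A, B and C with A+C as an added column. Alternatively, keep the pool, record it as a change to protocol-specified analyses with its reason, and bring the by-cohort wording in 2.1 and 2.3 into line.

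The cost is SAP wording, a few existing shells run on another analysis set, and extra columns. The drawback is small cell counts, so the tables should be read beside the patient listings.
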